We propose a prospective, open-label, single-arm pilot study treating 40 subjects to assess the hypothesis that P2Y12 inhibition with Brilinta/ticagrelor (90 mg PO twice a day) reduces episodic and/or chronic migraine headache symptoms in patients with right to left shunt. There will be no randomization or blinding of therapy. The study drug will be provided, free of charge, by the manufacturer, Astra-Zeneca. All subjects will be treated with the same medical regimen, and will be treated at Columbia University Medical Center or one of Principal Investigators external offices. All subjects will have an initial visit that will include the completion of a screening questionnaire (inclusion/exclusion criteria), informed consent, transcranial Doppler screening, laboratory blood testing by venipuncture (approximately 15 cc of blood = 1 tablespoon), and instruction on the use of the daily headache log (see Appendix 1, Appendix 2). Over the next 28 days, the subjects will receive an e-mail/text reminder daily with a link to complete the headache log (see below). At a second study visit, following completion of the first baseline month, the study staff will review the subject's headache log material, will release those subjects with insufficient headache days in the screening month, will assign the remaining/eligible subjects to either the episodic or chronic migraine cohort, will distribute the study drug, will administer the Brilinta/ticagrelor loading dose, and will review the medication's proper use. After 7 days of treatment with Brilinta/ticagrelor, while still on therapy, subjects will be sent for additional laboratory testing (PRU test < 10 cc of blood by venipuncture). At the completion of the 28 days (+7 days) on Brilinta/ticagrelor, each subject will have a follow-up study visit within 7 days, before discontinuing medication. At the third study visit, headache logs will be reviewed with the study staff, results will be discussed, remaining medications and empty bottles will be returned, and adverse events will be reviewed. Headache frequency while on Brilinta/ticagrelor will be compared with the documented baseline for each subject. If the Brilinta/ticagrelor therapy was effective (> 50% reduction in monthly headache days), the subject could elect to continue therapy for an additional two months, while continuing to complete daily headache logs.

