Non-serious Adverse Event: any other adverse event that does not meet criteria for a serious adverse event.

Definitions of bleeding events are based on the PLATO Trial protocol²⁸, a previously published study comparing Brilinta/ticagrelor to clopidogrel.

- **Major Life-Threatening Bleeding** includes:
 - Any Fatal Bleed
 - Intracranial Hemorrhage
 - Intrapericardial bleed with cardiac tamponade
 - Bleeding resulting in hypovolemic shock or severe hypotension that requires pressors or surgery
 - Clinically overt or apparent bleeding associated with decrease in hemoglobin >5 g/dL
 - Bleeding requiring transfusion of ≥4 U whole blood or PRBCs
- **Other Major Bleeding** includes:
 - Bleed causing clinically significant disability (e.g., intraocular bleed with permanent vision loss)

- Clinically overt or apparent bleeding associated with decrease in hemoglobin >3 g/dL, but < 5 g/dL
 - Bleeding requiring transfusion of ≥ 2 , but < 4 U whole blood or PRBCs
- **Minor Bleeding** includes any bleeding requiring medical intervention but not meeting the criteria for major bleeding

Working Study Definitions:

- **Migraine Headache Day:** any study day in which headache symptoms occur. If a single headache lasts from the end of a calendar day into the beginning of the next, it would be considered a single headache day provided the event lasted less than 24 hours. If headache symptoms last more than 24 hours, it would be considered 2 Headache Days; more than 48 hours would be considered to be three days, etc. Aura alone ("Acephalic migraine") will not be considered a headache. The subject must experience headache pain.
- **"Responder" to Therapy:** $\geq 50\%$ reduction in the average number of monthly headache days during the month of therapy compared with participant's own baseline.
- **"Non-responder" to Therapy:** $< 50\%$ reduction in the number of monthly headache days during the month of therapy compared with participant's own baseline.
- **Platelet Inhibition:** This is a functional definition based on Platelet Reactivity. PRU Test Result (VerifyNow PRU Test, Accumetrics Inc. San Diego CA) of < 140 , while on therapy, will be considered a "positive" inhibitory effect of the medication. PRU results of $141 - 160$ will be considered a borderline response. PRU results > 161 will be considered a negative response.

Primary Study Endpoints:

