Baseline-Monitoring Phase (Phase 1): The subject will track her/his headaches daily for 28 days through an online survey tool (REDCap, licensed through Columbia University), to establish a baseline headache frequency. Each day, the subject will receive a text message/e-mail reminder to complete the daily headache log. The message will contain a link to log into the survey tool. During this phase, subjects will answer questions including presence or absence of headache symptoms, severity of headache symptoms, duration of symptoms, impact on daily activities, and use of rescue medication. Any headache lasting more than 24 hours will be counted as a second headache day. After 28 days of monitoring, the study coordinator will assess the subject's data to make sure the subject meets criteria for minimum headache days, and has been consistently performing the daily log. If the number of headache days is insufficient, the subject's participation will be completed. If the subject logs at least 6 headache days in the month, she/he will continue in the study. If the participant has been assigned to the Episodic arm of the study, but has >14 headache days in the screening month, or if the participant has been assigned to the Chronic arm of the study, but has <15 headache days in the screening month, she/he will NOT be reassigned, but will remain in the assigned group for analysis. The subject will then be treated with Brilinta/ticagrelor for a 28-35 day test period (Phase 2). The length of the test period will depend on the timing of the participant's follow-up visit after beginning treatment. The protocol window is 28+7 days.

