Based on the known safety profiles of the clinically approved medication, Brilinta/ticagrelor will be given by mouth, in a dose of 90 mg twice daily. There are small, but known risks of this medication, particularly related to bruising and bleeding (see package insert). Since the potential benefits of the therapy is unknown in this application, the standard clinical dosing was selected.

There are several important pharmacologic differences between Brilinta/ticagrelor and the thienopyridines:

- Unlike the thienopyridines, Brilinta/ticagrelor binds reversibly to P2Y12
- Unlike the thienopyridines, in vivo metabolism is not required to have this effect.
- In pharmacodynamics studies, Brilinta/ticagrelor provided more potent and faster onset of platelet inhibition than clopidogrel, without a significant increase in the overall risk of major bleeding.²⁸

Several side effects, not seen with clopidogrel or prasugrel, were seen with the use of Brilinta/ticagrelor.

- Dyspnea³⁰⁻³² was usually mild and self-limiting with no change in pulmonary function tests. In PLATO it was seen in 14% of patients, compared with 8% of patients on clopidogrel.²⁸
- Bradyarrhythmia, particularly sinus pauses occurred in 5.8% of patients on Brilinta/ticagrelor and on 3.6% of patients on clopidogrel²⁸ with no clinically reported dizziness, syncope, pacemaker need or cardiac arrest. This effect is likely related to the drug's delay of adenosine metabolism and re-uptake.
- Increased serum levels of uric acid: as uric acid is a break-down product of adenosine, this is also likely related to higher levels of adenosine.
- Increased serum creatinine: These changes were not clinically apparent. Elevated adenosine levels also may explain this effect. Adenosine alters renal hemodynamics by decreasing tension in the afferent arteriole, and lowering the glomerular filtration pressure.

Packaging of Study Drug:

Brilinta/ticagrelor will be provided to the study by the manufacturer in its FDA approved packaging. The receipt, storage and dispensing of the investigational medication will be handled by the Research Pharmacy at Columbia University Medical Center. Medication bottles will be labeled as per federal and state regulations.

Storage and Distribution:

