Patients who meet Preliminary criteria will be consented by a member of the treatment team. At the first screening visit, patients will sign a Screening Consent, which will give the investigators permission to perform the Transcranial Doppler Study and blood work to assure their eligibility. Once it is determined that a right to left shunt is present, the complete consent for the TRACTOR Migraine Headache Study will be completed. All questions regarding the study will be answered and the patient will have the opportunity to discuss any research related issues. No time limit will be defined and sufficient time will be given to the patient to consider participation. The patient will be given the opportunity to consult with others including family members, referring physician, etc. If she/he is interested in participating, written consent will be obtained either at that time or at any subsequent date.

SAFETY AND ADVERSE EVENTS:**Definitions of Adverse Events (see above):****Recording of Adverse Events:**

The Principal Investigator will review all adverse events and immediately be notified of any Serious Adverse Event (SAE); an electronic Adverse Event Report Form will be completed.

Adverse Event Reporting Period:

Serious Adverse Events, after assessment by the study investigator, are to be reported to all other investigators (Executive Committee) within 48 hours. The Investigator will convene the Executive Committee to review/adjudicate the event, with reporting to the IRB/FDA/AstraZeneca as required. Non-serious adverse events will be recorded in the participant study record, reviewed by the study investigator, and will be reported to the IRB/AstraZeneca as required.

Reporting of Serious Adverse Events:

The Principal Investigator is responsible for concurrently informing AstraZeneca, as well as the local authorities and ethical committees, of any serious adverse events as per local requirements. Serious adverse events that do not require expedited reporting need to be reported to AstraZeneca quarterly either as individual case reports or as line-listings.

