Appendix 1:

Trial Schedule: (see attached TRACTOR Migraine Trial Flow Sheet in Appendix 2)

Study Visit #1: At the time of the first visit, study coordinator/investigators will discuss trial and subject eligibility for participation based on migraine headache frequency. The coordinator will collect all demographic information required for the study. Participant will receive explanation of the additional testing required for trial participation. After patient has been given an opportunity to ask questions, a screening consent will be signed to perform this testing. Participant will receive a Patient Study Number. Transcranial Doppler study will be performed. If negative for right to left shunt, participant will be sent back to the referring physician for on-going clinical care. If positive for right to left shunt (Spencer Grade ≥ 2) participant will be eligible to continue in the trial. The trial will be explained in detail, including participant responsibilities, and the patient will receive written study materials. A complete TRACTOR Migraine Headache Trial consent will be signed. The participant will receive a test e-mail/text message and must demonstrate the ability to answer the headache log questions. A Quality of Life Survey will be taken. Laboratory screening is done. End of visit.

Study Phase 1:
(28 Days) Within 72 hours of the laboratory evaluation, participant will be notified of results of laboratory testing and ability to continue participation. She/he will begin to receive daily reminders (e-mail/text message) to log-in to answer the headache log questions. A follow-up appointment will be scheduled within 7 days of the completion of 28 days of headache monitoring.

Study Day 29: Headache log entries will be reviewed by the Study Coordinator to determine final eligibility for trial based on the number of headache days documented.

Study Visit #2: Must occur within seven days of completion of baseline headache log. Participant will return to receive her/his medication. She/he will receive a loading dose of 180 mg of Brilinta/ticagrelor and an additional 70 tablets and will again review the responsibilities for participation with the coordinator. The participant will be observed for 30 minutes after taking the first medication dose.

Study Phase 2:

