(28-35 Days) Participant will receive reminder text message/e-mail to take daily study medication, and to log-in to answer the headache log questions. Participant will take Brilinta/ticagrelor 90 mg twice daily for 28-35 days. Participant will receive instructions for PRU testing.

PRU Testing: (> 7 days on drug)	Participant will go to local laboratory or to study center for blood testing of platelet inhibition.
Study Visit #3:	Within 7 days of completion the 28 th day of the study medication participant will return to meet with the study coordinator to review the results of the therapy, to return unused medication, and to review any adverse events. If no perceived benefit, participation is completed. If subject has had a clinical benefit, options for on-going therapy with additional headache log entries will be discussed. Participant will complete a follow-up Quality of Life questionnaire.
Continued Access (56-63 days):	If eligible, participant will continue to take Brilinta/ticagrelor for an additional 2 months. She/he will continue to receive daily e-mail/text message reminders to log-in to record headache data.
Study Visit #4:	Within 7 days of the 56 th day of study medication, participant will return to meet with the study coordinator to review the results of the therapy, to return unused medication, and to review any adverse events. Participant will complete a follow-up Quality of life questionnaire. Study is complete.

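### Scheduled adverse-event enquiry is limited to Visits 3 and 4, so non-serious reactions that are endpoints may be under-captured, although a daily survey already reaches every subject

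*Combined protocol and SAP*

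**What the plan says.** **Scheduled enquiry.** Study Design and Statistical Procedures places the review at the third visit: "remaining medications and empty bottles will be returned, and adverse events will be reviewed". The Treatment Phase text likewise has side effects reviewed at that visit. Appendix 1 describes the purpose of both Visit 3 and Visit 4 in part as "to return unused medication, and to review any adverse events". No other visit description includes such a review, and the flow chart in Appendix 2 has no adverse-event row. Visit 4 exists only for subjects who respond and choose to continue.

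**Other scheduled contact on drug.** At Visit 2, "The participant will be observed for 30 minutes after taking the first medication dose". The platelet reactivity (PRU) test after at least 7 days is described only as a blood draw, possibly at a local laboratory. A telephone call follows two consecutive missed log-ins, and its stated trigger is log compliance.

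**Daily log.** The Phase 1 text says the questions include "presence or absence of headache symptoms, severity of headache symptoms, duration of symptoms, impact on daily activities, and use of rescue medication". Headache Log Recordings adds that the log is finished for the day if there was no headache, and that the further questions on headache days concern that headache.

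**Between-visit routes.** Under Recording of Adverse Events, "The Principal Investigator will review all adverse events and immediately be notified of any Serious Adverse Event (SAE"). The Monitoring Plan has safety data reviewed on receipt and makes the coordinator the central contact for adverse events.

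**Endpoints.** Secondary Study Endpoints lists minor bleeding, allergic reactions, shortness of breath, rash and extreme fatigue. Statistical Considerations goes further and counts bleeding and adverse medication reactions over three months as a primary safety endpoint.

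**The concern.** Mild, short-lived symptoms are the kind most easily lost when a subject is first asked about them weeks later. Here they are named endpoints, and the plan has no scheduled way of collecting them close to the time they occur.

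Three uses of the data depend on that collection. The Executive Committee meets monthly to review safety, but for subjects still within Phase 2 it may have no solicited non-serious data to look at. Potential Risks plans a comparison of outcomes with historical data to detect new or unexpected events, and states that there is no prior report of this drug in migraine. The pilot is also meant to inform a larger randomized trial, including expected drop-out from side effects. If tolerability is recorded too favourably, the later trial is planned on the wrong footing, and symptoms that were not recorded at the time cannot be recovered.

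**Working it through.** **1. Recall intervals from the schedule.**
- First dose to Visit 3: 28 to 35 days, or 28/7 = 4 to 35/7 = 5 weeks. This applies to every subject who completes Phase 2.
- Visit 3 to Visit 4: 56 to 63 days, or 56/7 = 8 to 63/7 = 9 weeks. This applies only to responders who continue.
- After the last visit: Adverse Events Definitions counts events as study-related until 30 days after the last dose, but no contact is scheduled in that period.

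**2. What each channel can pick up.**

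| Channel | Asks the subject about non-serious symptoms? |
|---|---|
| 30-minute observation at Visit 2 | First half hour only |
| Daily log | No; headache items only |
| PRU blood draw | Not described |
| Missed log-in call | Not described |
| Immediate SAE notification | No; serious events |
| Coordinator as central contact | Receives reports; no enquiry described |
| Visit 3 and Visit 4 | Yes |

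**3. The plan's own bleeding figure.** Table 1 gives 4.5% major and 2.1% fatal or life-threatening bleeding on ticagrelor in PLATO, and the text puts about half of the events in the first 30 days.
- Major: 4.5% × 0.5 = 2.25% (stated as about 2.2%).
- Life-threatening: 2.1% × 0.5 = 1.05% (stated as about 1%).

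Both reproduce.

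**4. Major bleeding in 40 subjects.** With p = 2.25% and capture fraction c, expected recorded events = 40 × p × c, and P(none recorded) = (1 − p × c)^40. The values of c are assumptions.

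| c | Expected recorded | P(none recorded) |
|---|---|---|
| 100% | 0.90 | 0.40 |
| 80% | 0.72 | 0.48 |
| 50% | 0.45 | 0.64 |

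Even with full capture, 0 of 40 has an exact (Clopper-Pearson) 95% interval of 0 to 8.8%, which contains both 2.25% and 4.5%. The sample size dominates here.

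**5. Dyspnea in 40 subjects.** Dose Rationale and Risk/Benefits quotes 14% in PLATO. Expected recorded cases = 40 × 0.14 × c.

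| c | Expected recorded | Recorded rate |
|---|---|---|
| 100% | 5.6 | 14% |
| 80% | 4.5 | 11.2% |
| 50% | 2.8 | 7% |

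For a common mild reaction, incomplete capture can remove a material part of the count. The documents give neither c nor the exposure time behind the 14%, so the table illustrates the effect and does not predict it.

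**The case against.** **Routes between visits exist.** Serious events are notified at once, data are reviewed on receipt, and the coordinator can be contacted throughout. This stands for serious events. For non-serious symptoms these routes wait for the subject to speak up.

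**The forms are not in the documents.** The list of log questions comes from the Phase 1 text and is introduced as a partial list. A symptom item on an unseen form cannot be excluded. Headache Log Recordings nevertheless describes a log that closes on headache-free days.

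**A reader might infer that bleeding rates are under-counted against PLATO because no hemoglobin is drawn on drug.** The documents do not support this. The criterion is "Clinically overt or apparent bleeding associated with decrease in hemoglobin >5 g/dL", and the lower-threshold criterion is built the same way, so a routine value without overt bleeding could not create a major bleed. Minor bleeding is defined by need for medical intervention, which makes it harder to overlook than a passing symptom. A single extra tube at the PRU draw would also miss every later bleed.

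**A reader might also infer that creatinine must be re-measured.** The plan names creatinine rise as a drug effect, but it is not an endpoint, and Other Potential Risks considers it and regards it as less important in this population.

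**Recorded dyspnea might be said to fall below the 8% quoted for clopidogrel.** That happens only if capture is under 8/14 = about 57%; at 60% it is 14% × 0.6 = 8.4%. Nor are PLATO's collection methods given. Daily prompting here could bias a comparison in the opposite direction. With 40 subjects the intervals overlap widely in any case: 3/40 gives 1.6% to 20.4%, and 6/40 gives 5.7% to 29.8%.

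**Bradyarrhythmia does not help the argument.** The plan reports those episodes without clinical symptoms, so a symptom question would not find them.

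**A longer treatment-phase diary would differ from the baseline diary** on which the within-subject primary endpoint rests. This is a fair objection, and asking the item in every phase meets it.

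**Conclusion.** The concern holds for non-serious reactions. Scheduled enquiry is confined to Visit 3 and, for continuing responders, Visit 4, and everything between depends on spontaneous report. Shortness of breath, rash, extreme fatigue and minor bleeding may be under-captured. The direction is plausible but the amount is unknown: for dyspnea, anywhere from 5.6 down to 2.8 expected recorded cases in 40 over the assumed 100% to 50% range, and only if PLATO's 14% carries over to this population and exposure.

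The concern does not extend to major bleeding, where no under-count is shown and 40 subjects are too few for a sharp comparison under any collection method. It does not establish a bias in a known direction relative to PLATO, and it gives no case for routine hemoglobin or creatinine sampling. Because the results are declared descriptive, no formal inference is at risk. The loss is in the quality of the tolerability description handed to the next trial. This is a low-cost improvement worth making before enrolment.

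**What to change.** 1. Add one short item to the existing daily REDCap survey, placed before the headache question so that it is answered on headache-free days too: any new bleeding, breathlessness, rash, extreme fatigue or other new symptom since the last entry.
2. Ask it in Phase 1 as well as Phases 2 and 3. The diary then stays the same throughout, and Phase 1 supplies a pre-drug rate for symptoms that people with migraine may report anyway.
3. Route positive answers to the coordinator for entry on the adverse-event form, so that dated reports are available to the monthly Executive Committee meeting.
4. In the analysis plan, report solicited and spontaneously reported events separately, so that the historical comparison is not distorted by daily prompting.

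**Cost.** One extra answer per entry: up to 28 + 35 = 63 per subject through Phase 2, and 63 + 63 = 126 for those who continue. The log becomes slightly longer, which matters because log compliance is itself a feasibility outcome. More minor events will be recorded and followed up, and the tolerability figure is likely to look less favourable. No extra visit or blood sample is needed.

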Data collected from these 40 subjects will be evaluated to assess the feasibility of conducting a randomized, placebo-controlled, double blinded study in this population.

TRACTOR Migraine Trial Definitions

Headache Definitions:

(From: the International Classification of Headache Disorders (ICHD-II)
<http://www.ihd-classification.org/en/>)

- **Migraine without aura:** Requires all of the following symptoms: a) recurrent headaches (at least 5 lifetime attacks); b) untreated or unsuccessfully treated headache duration of 4 to 72 h; and c) at least two of the following pain characteristics: unilateral, pulsating, moderate or severe intensity, or aggravated by routine physical activity. In addition, the migraine attacks are associated with at least one of nausea/vomiting, photophobia, or phonophobia. Finally, other causes of headache must be excluded.
- **Migraine with aura:** Recurrent disorder manifesting in attacks of reversible focal neurological symptoms that usually develop gradually over 5-20 minutes and last

for less than 60 minutes. Headache with the features of migraine without aura usually follows the aura symptoms. Less commonly, headache lacks migrainous features or is completely absent.

- **Acephalic Migraine:** Migraine aura without subsequent head pain.
- **Episodic migraine:** migraine headaches as defined above, with history of 0 to 14 headache days per month.
- **Chronic migraine:** migraine headaches as defined above, with history of 15 or more headache days per month.

Adverse Events Definitions:

- **Adverse Event:** Any symptom, sign, illness or experience that develops or worsens in severity during the course of the study including intercurrent illnesses or injuries, whether or not it is considered therapy related. Adverse events will be reviewed by the Principal Investigator and the Executive Committee and will be defined as serious, or non-serious. Any adverse event will be considered “study-related” if it occurs in the time between the first dose of the study medication and 30 days after the last dose of the medication.
- **Serious Adverse Event:** Any adverse event that:
 - is fatal
 - is life-threatening requiring immediate intervention
 - requires or prolongs existing hospital stay
 - results in persistent or significant disability or incapacitation
 - requires intervention to prevent the above and/or permanent impairment or damage

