Treatment Phase (Phase 2): The subject will return for a follow-up visit to receive her/his medication within 1 week of completing the 28 day headache log. A loading dose of Brilinta/ticagrelor 180 mg will be administered in the office. Thereafter, for 28-35 days, a Brilinta/ticagrelor 90 mg tablet will be taken once in the morning and once in the evening, as close to 12 hours apart as possible. Each day, the subject will receive a text message reminder to login to the website, to record her/his headache activity. If she/he fails to login for two consecutive days, the study coordinator will place a follow-up phone call. PRU testing will be done a minimum of 7 days after the initiation of treatment, but before the medication is completed. A follow-up visit will be arranged between day 28 and day 35 days of monitoring to review efficacy, compliance, and side effects, to return unused medication, and to allow continued access to Brilinta/ticagrelor if indicated. A second Quality of Life survey will be completed.

Continued Access Phase (Phase 3): If the subject has a beneficial response to the Brilinta/ticagrelor (> 50% reduction in the average number of monthly headache days compared with the baseline), she/he will be offered continued access to the medication to complete an additional 2 months of therapy with on-going headache monitoring. A final office visit and Quality of Life Survey will be completed within 7 days of the 56th day of Phase 3 for return of unused medication, empty medication bottles and discussion about future therapeutic options. If the subject fails to have a beneficial response following the first month of treatment (Phase 2), the medication will be discontinued and participation in the study will be completed. If the subject elects to discontinue the Brilinta/ticagrelor, despite a beneficial response, participation in the study will be completed.

Outcomes Assessment/Statistical Analysis

Information from this study will be assessed to determine the feasibility of performing a larger randomized, blinded, placebo-controlled multi-center trial. We will assess not only our therapeutic drug response rate in order to estimate a required sample size for the future trial, but also our ability to recruit patients from local referring sources to estimate the time frame of such a trial. Subject compliance rate with use of daily online questionnaires will be determined. Drop-out rates, related to medication side effects will also be assessed.

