There may be circumstances in which a participant may need to withdraw from the TRACTOR Migraine Trial. These may include either Serious or Important Adverse Events (as listed above), a change in health status (including need for urgent surgical or medical intervention, or unanticipated pregnancy), or non-compliance with the protocol. Non-compliance would be defined as recurrent failure to take the medication as directed, failure to keep protocol appointments, or repeated failure to enter headache log information despite reminders from the local study coordinator.

Any other serious adverse event, which might require discontinuation of the study drug, would require documentation of the issue by the local study team, with formal consultation with the Principal Investigator. An electronic Patient Withdrawal Form would need to be completed by the Principal Investigator. Any adverse event leading to subject withdrawal will require documented discussion by the Executive Committee, and a follow-up assessment by the local study team, to confirm the participant's return to baseline health status.

Once withdrawn from the TRACTOR Migraine Trial for medical reasons, all efficacy data collected to date will be maintained, but no further data will be collected. Any participant who completes the daily headache logs for at least two weeks while on treatment, but who does not complete the full four weeks of the study period, will be classified according to their current response status (LOCF), regardless of whether or not they completed the required therapy (see Outcomes Assessment).

Should a participant choose to withdraw consent for the TRACTOR Migraine Trial, at any time during the monitoring period, for reasons other than an adverse event, the participant must contact the principal investigator, who will complete an electronic Patient Withdrawal

Form. In such a circumstance, efficacy data already collected will no longer be eligible for review. However, safety data up to the point of participant withdrawal will be reviewable for the final data analysis.

MEDICAL MONITORING

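### Adverse events count as study-related until 30 days after the last dose, but no scheduled contact collects them in that period

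*Combined protocol and SAP*

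**What the plan says.** Under TRACTOR Migraine Trial Definitions, an adverse event is study-related if "it occurs in the time between the first dose of the study medication and 30 days after the last dose of the medication". Under Reporting of Serious Adverse Events, every adverse event is to appear in the final report as a safety endpoint.

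The schedule runs as follows:

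- **Visit 3.** Study Design and Statistical Procedures states that "each subject will have a follow-up study visit within 7 days, before discontinuing medication". The Treatment Phase text gives the timing: "A follow-up visit will be arranged between day 28 and day 35 days of monitoring to review efficacy, compliance, and side effects". For a subject without a beneficial response, "the medication will be discontinued and participation in the study will be completed".
- **Visit 4.** Subjects in continued access are seen within 7 days of day 56 of a phase that Appendices 1 and 2 give as 56-63 days. Appendix 1 then declares the study complete.
- **After that.** The Appendix 2 flow chart has no later column: no visit, call or log.

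The section headed Adverse Event Reporting Period sets deadlines for passing reports on. It does not say how long events are collected.

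Two other safety windows are given. The primary safety endpoint is limited to time on the drug, and the Statistical Considerations measure safety over a three-month treatment period.

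For medical withdrawals, Withdrawal of Subjects says "all efficacy data collected to date will be maintained, but no further data will be collected". The paragraph before it requires a follow-up assessment after any withdrawal caused by an adverse event, without giving a date.

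**The concern.** The definition tells the trial to count events in the month after the last dose, but nobody is scheduled to ask about them. A bleed or reaction in that month enters the database only if the subject volunteers it. A report that applies the 30-day definition would then imply follow-up that was not planned, and a count of zero late events could mean either that none occurred or that none were asked about.

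This matters more than usual for a small pilot. The Potential Risks section says that use of this drug in migraine has not been reported before. Outcomes are to be compared with historical data to detect unexpected events, and the results may support a pivotal trial.

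**Working it through.** **Inputs**

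- Window: first dose to last dose + 30 days (Adverse Events Definitions).
- Phase 2: "Participant will take Brilinta/ticagrelor 90 mg twice daily for 28-35 days" (Appendix 1).
- Phase 2 supply: "loading dose of 180 mg of Brilinta/ticagrelor and an additional 70 tablets" (Appendix 1).
- Phase 3: 56-63 days (Appendices 1 and 2).
- Treated subjects: 40 (Statistical Considerations).
- Assumption: the last dose falls on the day of the last visit. The documents do not state this outright.

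**Step 1. Check the plan's own figure.** 35 days x 2 tablets = 70 tablets, which is the number dispensed after the loading dose. The supply therefore fits a Visit 3 no later than day 35.

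**Step 2. Subjects who stop at Visit 3.** Share without planned contact = 30 / (days on drug + 30).

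- 28 days on drug: 30 / 58 = 52%
- 35 days on drug: 30 / 65 = 46%

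**Step 3. Subjects who complete Phase 3.** Days on drug run from 28 + 56 = 84 to 35 + 63 = 98.

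- 84 days: 30 / 114 = 26%
- 98 days: 30 / 128 = 23%

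**Step 4. Relax the assumption for Visit 4.** Suppose the drug stops on Phase 3 day 56 and the visit falls on day 63. Then 30 - 7 = 23 days are uncovered.

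- 28 + 56 = 84 days on drug: 23 / 114 = 20%
- 35 + 56 = 91 days on drug: 23 / 121 = 19%

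Visit 3 needs no such variant, because the text places it before the drug is stopped.

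**Step 5. Whole trial.** Under the Step 2 and 3 assumption, 40 x 30 = 1,200 person-days have no planned contact. The share of all person-days in the window lies between 52% (nobody continues, shortest Phase 2) and 23% (everybody continues, longest phases). The documents do not give the proportion who will continue.

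**Step 6. Look for follow-up outside the schedule.** There are two provisions: the undated assessment after an adverse-event withdrawal, and follow-up of pregnancies to their outcome. The coordinator is also the central contact for adverse events, which allows subjects to report but does not schedule any enquiry.

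**The case against.** The strongest reply is that the 30 days are a rule for attributing events, not an order for active surveillance. The primary safety endpoint covers time on the drug, the analysis plan refers to the treatment period, and adverse events are reviewed at Visits 3 and 4. The trial is a descriptive pilot of 40 subjects, and no sample size or decision rule depends on the post-dose month. This stands as far as the primary safety endpoint goes. It does not answer the point for adverse events overall, because all of them are to be reported and late ones are captured only passively.

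A reader might infer more than the documents support in four respects:

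- **That the off-drug month is never observed.** Subjects can report events, and two groups have follow-up provisions. The accurate statement is that no contact is scheduled.
- **That every last visit is on drug.** This is explicit for Visit 3. For Visit 4 it is only implied by the 56-63 day phase.
- **That subjects withdrawn for an adverse event are dropped from safety follow-up.** They have an explicit assessment. The sentence on no further data opens with efficacy data and is followed by the efficacy carry-forward rule, so it can be read as limited to efficacy. The wording is loose, and the assessment has no date.
- **That about half of the safety events are missed.** The percentages weight every calendar day equally. The documents give no event rate after stopping and describe the drug as binding reversibly, so the number of missed events cannot be estimated.

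**Conclusion.** The concern holds in a limited form: the study-related definition has no matching scheduled collection point, so adverse-event capture after the last dose is incomplete by design. On the last-dose assumption above, the uncovered part is 46-52% of the window for subjects stopping at Visit 3 and 23-26% for those completing Phase 3. If Visit 4 came 7 days after the last dose, 23 days would still be uncovered. The figures describe subjects who follow the schedule. They do not cover early withdrawals. The gap affects overall adverse-event reporting and leaves the primary safety endpoint as worded untouched. It should be corrected because the remedy is small.

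**What to change.** 1. Add one scripted telephone or e-mail contact by the existing coordinator about 30 days after the last dose. Make it for every treated subject who has not withdrawn consent, including those withdrawn for medical reasons. Record it on the existing Adverse Event form and add it to both appendices.
2. In Withdrawal of Subjects, state that the rule on no further data applies to efficacy data only.
3. Reconcile the three safety windows (Adverse Events Definitions, Primary Study Endpoints, Statistical Considerations), so that the report says which events belong to which window.

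The cost is at most 40 short contacts and a brief amendment. If each contact asks about the whole 30 days, it covers up to 1,200 person-days that now have no planned enquiry. It falls about 58-65 days after the start of treatment for subjects stopping at Visit 3, and about 114-128 days for those completing Phase 3.
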